8. DATA ANALYSIS

To test hypothesis i, differences in physical activity levels will be examined using repeated measures analyses of covariance with baseline physical activity as the covariate. Where significant intervention x time interactions are found, post-hoc analyses will be conducted to determine the specific time point at which differences in physical activity between groups are found.

To test hypothesis ii, independent samples t-tests will compare post-intervention HAPA model constructs between groups.

To test hypothesis iii, we will use separate hierarchical regressions with change in physical activity entered as the predictor of change in arterial stiffness and secondary

health outcomes (cardiovascular, fitness).

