Research Design: This study will employ a multi-centre, randomized, wait-list controlled trial. A total of 30 participants (15 experimental, 15 wait-list control) between 18-65 years of age who have chronic $SCI \ge 1$ year prior will be recruited. Physical activity measures will be taken using wrist-based accelerometers and the Physical Activity Recall Assessment for Persons with SCI. Psychosocial factors will be evaluated through questionnaires. The primary health outcome measure (aPWV), and secondary cardiovascular parameters will be assessed using a combination of echocardiography and ultrasound. Fitness will be determined using a peak oxygen consumption test on an armcycle ergometer. All measurement will be taken at baseline and after 9 weeks following intervention commencement. Physical activity will also be sampled mid-intervention at 4 and 7 weeks. For the wait-list control group, an additional measurement time point will be added after they have received the intervention upon completion of the control period. Training will involve weekly, 10-15 minute coaching sessions for 9 weeks. All pre- and post-assessments will take place at the Blusson Spinal Cord Centre at ICORD or the University of British Columbia Okanagan. Intervention content will be delivered over Skype or phone, and the wrist- worn accelerometers will be delivered and picked up from the participant's home during the intervention.

Statistical Analyses: Analyses will be conducted to determine the training (time), group (control vs experimental) and interaction (time x group) of all indices.

Table of Contents

SUN	/IMARY	. 2
Prea	amble	. 5
1.	BACKGROUND AND PROGRAM RATIONALE 1.1 Physical inactivity and spinal cord injury (SCI) 1.2 Physical inactivity and cardiovascular disease (CVD) in spinal cord injury (SCI) 1.3 The Health Action Process Approach and physical activity interventions in spinal cord injury.	5 5 5 d 6
2.	PURPOSE & HYPOTHESES	. 6
3.	RESEARCH DESIGN/ PROTOCOL	. 7
4.	RECRUITMENT	. 9
5.	OUTCOME MEASURES	10
Pi	rimary Outcome Measure: Physical activity 6.1.1: Physical Activity Recall Assessment for People with Spinal Cord Injury (PARA- SCI):	10 .10 .10
	6.1.2: 6-day Physical Activity Monitoring Period	10
	Measurement of energy expenditure during different sub-maximal wheeling speeds for calculation of moderate-vigorous physical activity during the 6-day physical activity	
	monitoring period	11

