2. PURPOSE & HYPOTHESES

Primary objective: To determine whether brief PA coaching sessions guided by the HAPA model can change PA behaviour and psychosocial factors in individuals with chronic (>1 years post-injury) spinal cord injury (SCI)

Secondary objective: To determine whether improvements in PA have beneficial effects on arterial stiffness (aortic pulse wave velocity, aPWV) and secondary health outcomes (cardiovascular, fitness) in individuals with chronic (≥ 1 years post-injury) SCI.

Hypothesis i: Physical activity levels will be higher in the experimental than the wait-list control group.

Hypothesis ii: Self-reported HAPA model constructs (e.g. action planning, self-efficacy) will be improved in the experimental group compared to the wait-list control group.

Hypothesis iii: Participants who report higher levels of PA will have greater improvements on arterial stiffness and secondary health outcomes (cardiovascular, fitness).

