3. RESEARCH DESIGN/ PROTOCOL

A multi-centre, randomized, wait-list controlled trial will be used to compare the effects of tailored PA coaching sessions *versus* no coaching on PA behaviour, psychosocial factors, and health outcomes. Eligible individuals will be randomly assigned (1:1) to either the experimental (PA coaching sessions) or wait-list control condition. Groups will be stratified by injury level, age, and site. The randomization sequence will be generated by a research assistant independent of the trial. For an overview of the protocol see Figure 1.

Figure 1. Study Overview

Day 1 testing measures include vascular measures (arterial pulse wave velocity, arterial structure, and flow mediated dilation; 30 minutes), cardiac structure and function measures (30 minutes), administration of the demographics and Health Action Process Approach model questionnaire (25 minutes), and a measurement of energy expenditure at different sub-maximal wheeling speeds to calibrate MVPA cut-points (35 minutes) for a total duration of 2 hours. Participants will be given an accelerometer to wear for the 6-day monitoring period (6.1.2) after which they will return for Day 2 testing.

Day 2 testing measures include administration of the PARA-SCI (45 minutes), a peak oxygen uptake test (45 minutes), and at baseline, the first PA coaching session will be

administered (30 minutes) whereas at post-test a semi-structured interview will be administered (30 minutes). Total duration of day 2 testing will be 2 hours. The intervention protocol is described below. During the intervention, physical activity will be sampled at two time points; accelerometer and PARA SCI data will be taken during week 4 and week 7. Following the intervention, follow-up assessments of physical activity will be sampled monthly for 12 months in the intervention group only using the Leisure Time Physical Activity Questionnaire.

INTERVENTION

Intervention Protocol:

Experimental participants will receive weekly PA coaching sessions. Each session will be 10-15 minutes in duration and delivered either face to face, over Skype, or when the former modes are unavailable, over the phone. These sessions will be recorded using a portable audio recorder. Additionally, supplemental resources may be emailed to the participants based on need throughout the intervention.

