Participants' motivation to exercise will first be determined according to stages of the HAPA model. Those who identify as pre-intenders (no intention to exercise) will receive intervention strategies that focus on changing motivation to be physically active. Those identified as intenders (willing to exercise but have not started) will focus on providing resources and behavioural strategies to commence physical activity. Lastly, those identified as actors (already exercising) will receive intervention strategies that help participants maintain or improve PA behaviour.

For those in the intender or actor stage, the intervention aims to promote the international SCI PA guidelines to promote fitness (at least 20 minutes of moderate vigorous aerobic activity twice/week and strength training twice/week). For those exceeding the fitness guidelines, the international SCI PA guidelines to promote health are promoted (at least 30 minutes of moderate to vigorous aerobic activity three times/week and strength training twice/week). However, these aims will be modified based on the individual's baseline PA. During the first visit, participants' baseline PA levels will be reviewed and an appropriate PA goal to achieve in the following month will be formed. In line with small changes PA goal setting, no pre-set goal grading strategies are established.²² In general, the goal of increasing daily PA by ten minutes on at least two days/week is provided as a guideline for grading the increase in goals. However, ultimately, the goal is the decision of the participant.

Following goal setting, barriers to participating in PA will be identified. The interventionist will select intervention strategies based on the identified barriers. A preformed chart of corresponding intervention strategies (e.g. use of behaviour change techniques, referral to facilities or peers, suggesting at-home exercises) was developed to aid this pairing process (Appendix A). These intervention strategies are accompanied by a comprehensive toolkit based from the HAPA model (Appendix B). In brief, the toolkit advises on three key strategies for promoting PA to people with SCI: i) education, ii) referral, iii) tailored PA prescription.

Remaining weekly coaching sessions will review participants' progress and barriers to discuss new goals and strategies as outlined above.

Control Participants:

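### Section 8 names no deciding term for hypothesis i, and it reaches time-point comparisons through an interaction that, on the ordinary reading of a baseline-covariate model, does not carry the treatment effect powered in section 4

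*Combined protocol and SAP*

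**What the plan says.** Hypothesis i (section 2) is about level: "Physical activity levels will be higher in the experimental than the wait-list control group". For this hypothesis, section 8 says that "differences in physical activity levels will be examined using repeated measures analyses of covariance with baseline physical activity as the covariate". It then continues: "Where significant intervention x time interactions are found, post-hoc analyses will be conducted to determine the specific time point" at which the arms differ. It gives no other route to a comparison at a particular week, lists no levels of time and names no deciding term. The Summary (Statistical Analyses) does not choose either: "Analyses will be conducted to determine the training (time), group (control vs experimental) and interaction (time x group) of all indices".

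The sample size paragraph in section 4 powers a condition-by-time effect of d = .75 in a repeated measures ANOVA, with 12 per condition, power .80 and alpha .05.

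On visits, the Summary says "All measurement will be taken at baseline and after 9 weeks following intervention commencement" and "Physical activity will also be sampled mid-intervention at 4 and 7 weeks". Section 3 says of the intervention period that "accelerometer and PARA SCI data will be taken during week 4 and week 7". Its paragraph on control participants limits that arm to baseline and post-test.

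**The concern.** Sections 4 and 8 use the same name for what may be two different tests. In a repeated measures ANOVA with baseline as one level of time, condition by time is the treatment effect: the arms start together and separate. Once baseline becomes the covariate and only post-baseline visits remain as levels, that effect moves to the group term. The interaction then measures only whether the arm difference changes from visit to visit.

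A benefit present by week 4 and held to week 9 is what hypothesis i describes, yet it would produce no such interaction. Following section 8 as written, the team would usually not reach the week-9 comparison. With time, group and interaction all listed and none chosen, the deciding test could also be picked after the data are seen, in a trial with 12 to 15 people per arm.

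**Working it through.** **1. The plan's own figure.** Section 4 gives d = .75, N = 24, power .80 and alpha .05. It does not give the standardiser or the within-person correlation ρ. Two sets of assumptions reproduce N = 24:

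- Take f = d/2 = 0.375 with two levels of time, so λ = f²·N·2/(1 − ρ). At ρ = 0.25, λ = 0.140625 × 24 × 2/0.75 = 9.0 and power is 0.818. N = 24 is the smallest even N reaching 80% for ρ of 0.22 to 0.28.
- Take d in SD units of the outcome and a t-test on change, with SD of change √(2(1 − ρ)). At ρ = 0.81 this is √0.38 = 0.616. The noncentrality is (0.75/0.616) × √(12/2) = 2.98 on 22 df, and power is 0.813. Twelve per arm is the smallest n for ρ of 0.81 to 0.82.

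The figure is attainable. Both routes treat baseline as a level of time.

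**2. Where the effect sits if time means weeks 4, 7 and 9 in both arms.** Let δ4, δ7 and δ9 be the baseline-adjusted arm differences. The group term estimates their mean. The interaction tests whether they are equal.

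Assumptions not in the documents: effects in SD units of the outcome, compound symmetry, ρ = 0.5 or 0.7, two-sided 0.05. With n = 12 per arm:

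- Interaction (2 df): λ = (n/2)·Σ(δt − mean)²/(1 − ρ).
  - Sustained 0.75/0.75/0.75: the sum is 0, so λ = 0 and rejection is at the alpha rate.
  - Building 0.25/0.50/0.75: the sum is 0.125, so λ = 6 × 0.125/0.5 = 1.5, or 6 × 0.125/0.3 = 2.5.
  - Later onset 0/0.375/0.75: the sum is 0.28125, so λ = 3.375 or 5.625.
- Week-9 ANCOVA: SE² = (2/n)(1 − ρ²)(1 + 1/(2n − 4)), with 2n − 3 = 21 df.
  - ρ = 0.5: 0.1667 × 0.75 × 1.05 = 0.131, SE 0.362, noncentrality 0.75/0.362 = 2.07, power 0.506.
  - ρ = 0.7: 0.1667 × 0.51 × 1.05 = 0.0893, SE 0.299, noncentrality 2.51, power 0.668.
- Averaged group term: replace (1 − ρ²) by (1 + 2ρ)/3 − ρ², which is 0.417 or 0.31. For a sustained effect the noncentrality is 2.78 or 3.22.

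Results at ρ = 0.5 / 0.7, 12 per arm. The week-9 column is by formula for the first three shapes; the rest is by simulation (6,000 to 8,000 trials per scenario):

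| Effect at weeks 4/7/9 | Gate opens | Week-9 ANCOVA, ungated | Averaged group term | Gate opens and week 9 significant |
|---|---|---|---|---|
| Sustained 0.75 | 5% / 5% | 51% / 67% | 75–76% / 87% | 2% / 3% |
| Building 0.25/0.50/0.75 | 16–17% / 24–25% | 51% / 67% | 43% / 53–54% | 13% / 21% |
| Later 0/0.375/0.75 | 32% / about 50% | 51% / 67% | 27% / 34% | not run |
| Fading 0.75/0.50/0.25 | 16% / 24–25% | 10% / 13% | 43% / 54% | 1% / 1% |

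Repeat simulations put the week-9 ANCOVA at 50–68% for the first three shapes. With 15 per arm the gate opens in 5–6% (sustained) or about 20–31% (building).

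A building effect is a realistic case, because the weekly sessions review "progress and barriers to discuss new goals and strategies as outlined above".

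**3. If baseline is also a level of time.** With baseline and week 9 only, the interaction p-value equals the week-9 ANCOVA group p-value (largest difference 1.3e-15 in 300 simulated data sets). With four levels (baseline, 4, 7, 9) and baseline also as covariate, the interaction has about 47% / 69% power for the sustained effect and about 34% / 54% for the building one.

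**4. If controls have baseline and week 9 only.** The model has 1 + 1 + 2 + 2 + 1 = 7 columns (intercept, group, time, group by time, baseline). The design then has rank 5, so the interaction cannot be estimated.

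**The case against.** The strongest reply is that hypothesis i is not gated. The Summary lists the group term, which has 75–87% power for a sustained effect. When the effect is truly constant there is no particular week to locate, so a closed gate is the correct answer to the question the interaction asks. This stands. A reader might infer that hypothesis i cannot be tested under section 8, and the documents do not support that. What remains is that the group term is not named as decisive and that no week-9 estimate is provided for unless the gate opens.

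Second, section 4 speaks of condition by time in a repeated measures ANOVA, so the authors may have kept baseline as a level of time as well as a covariate. The interaction would then carry the effect. It would be too strong to say that it never does. Section 8 does not state that model, however, and its result depends on the unstated choice.

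Third, a reader might infer from the control-participant paragraph that the rule cannot be run at all. That is possible but not shown. Section 3 gives weeks 4 and 7 without restricting the arm, while it does restrict the 12-month follow-up to the intervention group. Section 8's reference to a specific time point also suggests several shared visits. Figure 1, not available in the text reviewed, may settle it.

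Fourth, how often the gate opens depends on the shape of the effect: a later onset opens it in up to about half of trials.

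Finally, the sample size might look wrong. It is not shown to be: step 1 reproduces it, although the assumptions needed are not stated.

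**Conclusion.** The point holds, conditional on the reading of time. On the ordinary reading of a baseline-covariate model, the interaction in section 8 is not the effect powered in section 4, and using it as the gate would usually withhold the week-9 comparison. At 12 per arm the gate opens in about 5% of trials (sustained), 16–25% (linear build-up) or 32–50% (later onset), against about 50–68% for an ungated week-9 ANCOVA. These figures rest on an assumed effect of 0.75 SD of the outcome, compound symmetry and correlation 0.5 to 0.7.

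The analysis is not void. The loss is the week-9 comparison and a deciding test fixed in advance. If baseline is also a level of time, the matter is mainly one of wording. Under every reading, section 8 still needs to name the deciding term and the levels of time.

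**What to change.** In section 8, name one baseline-adjusted between-arm contrast as the test of hypothesis i, not conditional on any interaction. The week-9 ANCOVA difference is the safe choice, because every reading of the visit schedule gives both arms that visit. If both arms are confirmed to have weeks 4 and 7, the group term averaged over the post-baseline visits is a valid alternative, provided it is chosen in advance. Report visit-specific differences as supportive, without the gate. If controls are not measured at weeks 4 and 7, describe those weeks within the coached arm only. Reconcile the Summary with the section 3 text on mid-intervention sampling and on control participants, and list the visits by arm.

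In section 4, restate the power for the named contrast, saying which SD d = .75 refers to and what correlation is assumed. The contrast also needs its PA measure named, since section 4 uses minutes per week and section 6.1.2 minutes per day.

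The cost is rewording, with no new data. There are two real downsides. Week 9 alone has less power than the averaged term if the effect is constant (51–67% against 75–87%) or fades (10–13% against 43–54%). The restated power may also fall below .80: with d in SD units of the outcome, 12 per arm reaches 80% for the week-9 contrast only at a correlation of about 0.79.

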Control participants will complete baseline and post-testing only. Following completion of post-test measures they will be administered the same PA coaching session as the intervention group, with post-test measures being repeated upon intervention completion.

Standardization across sites

The intervention will take place in Vancouver for the months of April to July and in Kelowna from August to October. The same equipment brand and model will be used between sites where available. All intervention content, psychological, and fitness measures will be delivered by the same researcher. Although vascular and cardiac measures will be administered by different researchers in Vancouver and Kelowna, all technicians are experienced in their respective techniques, decreasing the likelihood of human error.

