4. RECRUITMENT

A total of 30 participants with a chronic (>1 year post injury) spinal cord injury between 18-65 years of age will be recruited. Individuals must be competent to give informed consent, and be able to propel an arm ergometer.

Exclusion Criteria:

- History and/or symptoms of CVD or cardiopulmonary problems/disease.
- Major trauma or surgery within the last 6 months.
- Active Stage 3 or 4 pressure ulcer (based on the National Pressure Ulcer Advisory Panel classification)
- Recent (within 1 year) history of lower-extremity or non-union fracture
- Any unstable medical/psychiatric condition or substance abuse disorder that is likely to affect their ability to complete this study.
- Individuals with active medical issues such as pressure sores, urinary tract infections, hypertension, or heart disorders.
- Any cognitive dysfunction or language barrier that would prevent subjects from following English instructions.
- Subjects may be excluded at the discretion of the principal investigator due to other, unforeseen, safety issues.

Sample size calculation: Our study is powered to detect a significant condition X time effect for our primary outcome measure, min/wk of PA. A previous single-group study of adults with SCI tested the effects of a PA-enhancing intervention delivered by a peer and a fitness trainer (Latimer-Cheung et al., 2013). That study found very large, significant effects for change in min/wk of PA (d = .96). Given our two-group design, we are powering for a more modest interaction effect (d = .75). Twelve participants/condition (N = 24) are needed to yield a significant effect of this magnitude in a repeated measures ANOVA, with $\beta = .80$ and $\alpha = .05$. To account for study dropouts, we are budgeting for an N of 30.

Potential participants will be identified through a variety of recruitment strategies including: posters which will be distributed among hospital locations and local community venues (e.g. local sports venues, community program centres); social media advertising (i.e., website, Facebook, Twitter); email; and at the individual's request (some participants have previously provided consent to be contacted for future studies).

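### Hypothesis ii is tested on post-intervention HAPA scores alone, leaving the baseline scores collected in both arms unused and disagreeing with the Summary

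*Combined protocol and SAP*

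**What the plan says.** Section 8 (Data Analysis) gives one test for hypothesis ii: "independent samples t-tests will compare post-intervention HAPA model constructs between groups". No baseline term appears.

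The hypothesis in section 2 is worded as improvement: "Self-reported HAPA model constructs (e.g. action planning, self-efficacy) will be improved in the experimental group compared to the wait-list control group".

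Baseline HAPA scores exist in both arms:
- The Summary says "All measurement will be taken at baseline and after 9 weeks following intervention commencement".
- Section 3 lists the HAPA questionnaire among the Day 1 testing measures.
- For the wait-list arm, section 3 says "Control participants will complete baseline and post-testing only".

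Two other statements bear on the choice of analysis:
- For hypothesis i, section 8 uses "repeated measures analyses of covariance with baseline physical activity as the covariate".
- The Summary's statistical paragraph says "Analyses will be conducted to determine the training (time), group (control vs experimental) and interaction (time x group) of all indices".

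**The concern.** A post-only t-test estimates a group difference at one time point. It contains no time or interaction term, so it is not the analysis that the Summary describes for every index. With two analyses of the same constructs in the plan, the choice between them could be made after the results are seen.

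The second issue is efficiency. Psychosocial factors are named in the primary objective and labelled the secondary outcome measure, and the trial plans on 24 to 30 people. Randomisation is stratified by injury level, age and site, not by HAPA score or motivational stage. A chance difference between arms in baseline HAPA scores is therefore quite possible. If one occurs, a difference in post-intervention scores is hard to read as improvement. Baseline adjustment deals with this using data already in hand.

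**Working it through.** **Inputs from the documents.** 1:1 allocation (section 3). Twelve per condition needed and 30 recruited in total, so 12 to 15 per arm; α = .05; d = .75 for minutes per week of physical activity (section 4).

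**Assumptions.** The documents give no HAPA effect size, so d = .75 is borrowed for illustration. They give no baseline-to-post correlation r, so a range is shown. Tests are two-sided, scores are in SD units, and r is the same in both arms unless stated.

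**The plan's own figure.** There is none for hypothesis ii. The 12 per condition in section 4 is for physical activity under a repeated measures ANOVA whose correlation is not stated, so it does not bear on this point.

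**Step 1: power of the planned t-test.** Noncentral t with df = 2n − 2 and noncentrality d√(n/2).
- n = 12: .75 × √6 = 1.837, power .420.
- n = 15: .75 × √7.5 = 2.054, power .509.

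**Step 2: power of ANCOVA.** Noncentral t with df = 2n − 3 and noncentrality d / √[(1 − r²)(2/n)(1 + F/(2n − 2))], averaged over F ~ F(1, 2n − 2). The last factor allows for estimating the covariate slope.

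| r | n = 12 | n = 15 |
|---|---|---|
| t-test | .420 | .509 |
| 0 | .403 | .494 |
| .2 | .417 | .510 |
| .3 | .435 | .532 |
| .4 | .464 | .565 |
| .5 | .507 | .613 |
| .6 | .572 | .681 |
| .7 | .669 | .777 |

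Simulation with 100,000 trials per cell agrees within .003. The methods break even at r of about .22 (n = 12) and .19 (n = 15).

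**Step 3: precision, which does not depend on d.** The variance ratio of ANCOVA to post-only is (1 − r²)(1 + 1/(2n − 4)). At n = 12 the second factor is 1.05, which gives:
- r = 0: 1.05
- r = .3: .91 × 1.05 = .956
- r = .5: .75 × 1.05 = .788
- r = .7: .51 × 1.05 = .536

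The expected 95% confidence interval half-width at n = 12 is .84 SD post-only, against .86, .82, .74 and .61 SD at those four values of r.

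**Step 4: chance imbalance at baseline.** The standard error of the baseline difference is √(2/n): .408 at n = 12 and .365 at n = 15. The chance that it exceeds .5 SD in either direction is 2[1 − Φ(.5/.408)] = .221 and 2[1 − Φ(.5/.365)] = .171. When it does so at n = 12, its mean absolute size is .408 × φ(1.225)/[1 − Φ(1.225)] = .697 SD. The post-only estimate is then off by r × .697 on average: .14, .35 or .49 SD at r = .2, .5 or .7, in either direction.

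**Step 5: unequal correlations by arm.** Simulation at n = 12 and d = .75, 60,000 trials per cell, against 42% for the t-test:
- r = .5 in controls and 0 in the coached arm: ANCOVA 43%.
- r = .5 and .2: 45%.
- r = .7 and 0: about 45%.

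**The case against.** The strongest reply is that nothing here is an error. After randomisation, a comparison of post-intervention scores estimates the effect of coaching, is unbiased on average and holds its 5% type I error. Improvement relative to control is itself a between-arm contrast. That stands, and it limits the point to efficiency and clarity.

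The size of the gain rests on values that the documents do not give. At r = .3 it is only about 2 percentage points. Coaching is also tailored to motivational stage, which could weaken the correlation in the coached arm, and step 5 shows that the gain then shrinks to about 1 to 3 points. Both remarks are right: a gain is likely but not assured. Even so, ANCOVA was no worse than the t-test in any of the unequal-correlation cases tried.

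Steps 3 and 4 describe one mechanism from two sides, so their figures should not be added together. That also stands.

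The Summary sentence is generic, and section 8 is the specific text. The hypothesis iii regressions do not match that sentence either. The conflict is therefore a drafting matter, though one worth settling before data are seen.

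Finally, section 7 excludes participants who attend fewer than six of the nine sessions. Controls have no sessions before their post-test, so in this comparison the rule can remove only coached participants. The assurance that the t-test is unbiased therefore holds for the arms as randomised, not necessarily as analysed. Baseline adjustment may reduce such selection but cannot be relied on to remove it.

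**Conclusion.** The concern holds. Section 8 gives the baseline HAPA scores no role although both arms provide them, and its test differs from the analysis stated in the Summary. The planned test is valid for the randomised arms; the loss is one of precision.

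The trade-off favours adjustment. At 12 to 15 per arm and d = .75, ANCOVA costs less than 2 percentage points of power at r = 0. It gains about 9 to 10 points at r = .5 and about 25 to 27 at r = .7. These power figures rest on a borrowed effect size and a common correlation in both arms; the variance ratios and imbalance probabilities do not depend on d. The change should be made, but the trial does not fail without it.

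**What to change.** In section 8, replace the t-tests for hypothesis ii with an ANCOVA for each HAPA construct: post-intervention score as outcome, arm as factor and that construct's baseline score as covariate. Report the adjusted difference with its 95% confidence interval. Reword the Summary's statistical paragraph to match, so that only one analysis of the HAPA constructs is specified.

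The cost is one sentence in each place and one degree of freedom per model, with no new data and no added burden on participants.

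### Section 8 gives no between-arm analysis for arterial stiffness, VO2peak or any other health outcome, although section 3 and the Summary say the randomised groups will be compared on them

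*Combined protocol and SAP*

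**What the plan says.** Section 3 (Research Design/Protocol) describes a trial in which "Eligible individuals will be randomly assigned (1:1) to either the experimental (PA coaching sessions) or wait-list control condition". It gives the purpose as a comparison of tailored coaching with "no coaching on PA behaviour, psychosocial factors, and health outcomes". The Statistical Analyses paragraph of the Summary goes further: "Analyses will be conducted to determine the training (time), group (control vs experimental) and interaction (time x group) of all indices".

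Section 8 (Data Analysis) then takes the hypotheses one at a time.

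- Hypothesis i: "differences in physical activity levels will be examined using repeated measures analyses of covariance with baseline physical activity as the covariate", with follow-up of any intervention-by-time interaction.
- Hypothesis ii: "independent samples t-tests will compare post-intervention HAPA model constructs between groups".
- Hypothesis iii: "separate hierarchical regressions with change in physical activity entered as the predictor of change in arterial stiffness" and the other cardiovascular and fitness outcomes.

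Nothing else in section 8 concerns the health outcomes. The secondary objective in section 2 reads "To determine whether improvements in PA have beneficial effects on arterial stiffness" and the secondary health outcomes. Hypothesis iii predicts larger health gains in participants who report more PA, and mentions no arm.

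**The concern.** The first two hypotheses each get a comparison of randomised groups and the third gets none. The health outcomes are therefore left with an analysis whose exposure is something participants do after allocation. Section 3 leaves the final PA goal to the participant, so change in PA is in large part self-chosen. Pain, intercurrent illness or season could move both PA and fitness over nine weeks and produce a slope with no effect of PA behind it.

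At stake is what can be said about health at the end. The objective is worded causally, and section 3 promises a comparison of coaching with no coaching. If section 8 is followed literally, a significant slope might be reported as a health benefit of PA or of coaching, with no unconfounded estimate beside it.

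**Working it through.** **1. Promise against plan**

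| Outcome group | Between-arm comparison in section 3 | Summary (all indices) | Between-arm analysis in section 8 |
|---|---|---|---|
| PA | yes | yes | yes, repeated measures ANCOVA |
| Psychosocial (HAPA) constructs | yes | yes | yes, t-tests |
| aPWV, cardiovascular, fitness | yes | yes | none stated |

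**2. Are the data there?** Yes. The Summary schedules all measurements at baseline and nine weeks, and section 3 has control participants complete baseline and post-testing before they receive coaching. A week-9 comparison needs no new measurement.

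**3. Would putting arm into the regression solve it?** No. A simple model shows why; its inputs are assumptions. Let g = 1 for coaching and 0 for control, and let u be an unmeasured factor with variance 1. Set change in PA = 0.75g + u. Set change in health = r·u + noise, with total variance 1. PA then has no effect on health, and r is the within-arm correlation of the two changes. The 0.75 SD shift borrows the effect size in section 4 (Recruitment); no document gives a value for r.

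- Variance of change in PA over both arms: 1 + 0.75² × 0.25 = 1.141.
- Correlation without an arm term: r / √1.141 = 0.936r, that is 0.28 for r = 0.3 and 0.47 for r = 0.5.
- Correlation with an arm term: r itself, 0.30 and 0.50.

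The arm term removes the randomised part of PA change and leaves the self-chosen part, so the spurious association rises slightly. Simulated rejection rates at two-sided 0.05 (20,000 runs):

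| N | r | Regression, no arm term | Regression, arm term | Arm comparison |
|---|---|---|---|---|
| 24 | 0.3 | 27% | 29% | about 5% |
| 24 | 0.5 | 66% | 71% | about 5% |
| 30 | 0.3 | 32% | 36% | about 5% |
| 30 | 0.5 | 76% | 81% | about 5% |

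These rates illustrate the mechanism under the assumed r and shift. They do not forecast this trial.

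**4. Precision of the missing comparison.** The plan has no sample-size figure for health outcomes. Its 12 per condition (24, raised to 30 for dropout) is for PA at d = 0.75. That figure depends on an unstated within-person correlation: the two-time-point interaction formula with f = 0.375 gives N = 30, 22 and 18 at correlations of 0, 0.3 and 0.5. It cannot be called wrong, and nothing here rests on it.

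For a health outcome, take the two-sample t-test with two-sided alpha 0.05 and power 0.80, solving for d in the noncentral t with noncentrality d·√(n/2):

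- n = 12 per arm: d = 1.20.
- n = 15 per arm: d = 1.06.

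Baseline adjustment multiplies d by about √(1 − ρ²). At an assumed ρ = 0.7 the factor is √0.51 = 0.714:

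- 1.20 × 0.714 = about 0.85 (unrounded 1.197 gives 0.855).
- 1.06 × 0.714 = 0.76.

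The planned regression is not precise either. With r = tanh[(1.960 + 0.842)/√(N − 3)], the correlation detectable at 80% power is 0.55 at N = 24 and 0.49 at N = 30.

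**The case against.** The strongest reply is that the regression matches its hypothesis. Hypothesis iii is about participants with higher PA, and the secondary objective concerns improvements in PA rather than assigned coaching. An arm comparison answers a different question, and at this sample size answers it poorly. Most of this stands. The regression is a fair test of hypothesis iii as an association and should stay. An arm comparison estimates the effect of coaching, and speaks to PA only if coaching acts on health through PA. The reply does not remove the promise in section 3 and the Summary, nor the causal wording of the objective. Low precision is a reason to report an interval, not to omit the estimate.

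A reader might also infer more than the documents support:

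- **That the regression pools the arms and omits arm and baseline values.** Section 8 calls the models hierarchical, which implies blocks, but lists none. Nor does it say whether the wait-list group's data after its own coaching period are used. Pooling is a natural reading but an inference, and by step 3 the conclusion holds either way.
- **That the trial abandons its randomisation for health outcomes.** The Summary still commits to group and time-by-group tests. The commitment has not been made operational in section 8.
- **That the simulated percentages are false-positive rates for hypothesis iii.** They are the power to detect a correlation that was assumed. As an association, that correlation is real.

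**Conclusion.** The concern holds as a gap between promise and plan. Section 8 gives no between-arm analysis for any health outcome, while section 3 and the Summary say there will be one. This follows from the text and needs no assumption.

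That the slope cannot by itself support a causal claim about PA, or a benefit of coaching, rests on change in PA being a post-randomisation and largely self-chosen variable. The size of any resulting distortion is unknown, because the documents give no correlation between the changes. The analysis of PA, the primary outcome, is untouched, so this is a change that should be made rather than a fatal flaw.

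**What to change.** In section 8:

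1. Add, for each health outcome, an ANCOVA of the week-9 value by randomised arm, adjusted for the baseline value. For the wait-list group, use the post-test at the end of the control period.
2. Name aPWV as the lead health outcome. The Summary already treats it as the main health measure, and section 5 ranks it above the cardiovascular and fitness parameters. Report VO2peak and the other indices alongside it, all with confidence intervals.
3. Include all randomised participants with data. Do not apply the section 7 (Adherence) rule of at least 6 of 9 sessions to this comparison. Controls have no sessions in the control period, so the rule could remove only coached participants and would undo the balance from randomisation.
4. Keep the change-on-change regression for hypothesis iii, list its blocks, and label it an association.

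The cost is wording in the analysis section; every variable is already collected. The downside is imprecision: at the planned 12 evaluable per arm, only differences of about 1.20 SD unadjusted, or about 0.85 SD at the assumed baseline correlation of 0.7, would be detected with 80% power. The health claims will have to be correspondingly modest. If the sponsor does not want this comparison, the statements in section 3 and the Summary need narrowing instead.
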